12.3 Grading and Attribution of Adverse Events

12.3.1 Grading Criteria

12.3.1.1 Grading of Solicited Adverse Events

Participants will grade solicited AEs using a 0-3 participant symptom rating scale as outlined in the Vaccine Reaction Diary instructions (Appendix 20.3 Adult Vaccine Reaction Diary).

Participant Symptom Rating Scale

- 0 = No symptoms
- 1 = Mild: Present, but did not require over-the-counter or prescription medications; did not interfere with daily activities
- 2 = Moderate: Required over-the-counter or prescription medications; caused some interference with daily activities
- 3 = Severe: Required over-the-counter or prescription medications; significant, incapacitating discomfort preventing daily activities

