12.3.1.1.1 Grading of Pediatric Gastrointestinal Solicited Adverse Events

Pediatric participants will grade nausea, vomiting, and diarrhea solicited adverse events using a 0-3 symptom-specific rating scale as noted below and in the Vaccine Reaction Diary for Pediatric Participants (Appendices 20.4, 20.5, 20.6):

Nausea/Vomiting

- 0 = No symptoms
- 1 = Mild: 1 to 2 times in 24 hours
- 2 = Moderate: > 2 times in 24 hours
- 3 = Severe: Prevents daily activity

Diarrhea

- 0 = No symptoms
- 1 = Mild: 2 to 3 loose stools in 24 hours
- 2 = Moderate: 4 to 5 loose stools in 24 hours
- 3 = Severe: 6 or more loose stools in 24 hours

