20.3 Adult Vaccine Reaction Diary

ACV01 Vaccine Reaction Diary Card

Participant ID: _____

Study Doctor: _____

Phone Number: _____

Call the Study Doctor listed above:

- If you have a temperature equal to or greater than 102.4 °F
- If you have any severe symptom that prevents daily activity or requires medical care
- If injection site symptoms are noted larger than ring B on the measuring tool
- If you have any concerns or questions about completing the Diary Card or about any symptoms you are experiencing

PLEASE HAVE THIS DIARY CARD WITH YOU DURING EACH SCHEDULED CALL WITH STUDY STAFF

YOUR CALL IS SCHEDULED

ON: _____

AT: _____

AM / PM

TEMPERATURE RECORDING: Take and record your oral temperature daily. Aim to take your temperature at the same time each day. Record all temperatures in degrees Fahrenheit (°F).

Directions:

1. Wipe the thermometer clean with rubbing alcohol and rinse with cold tap water before and after each use.
2. Do not eat, drink any liquids, exercise, bathe, or smoke for at least 15 minutes before taking your temperature.
3. Press the On/Off button. You will see the last recorded temperature briefly. The thermometer is ready to use when it reads "Lo" and a blinking "°F" is visible.
4. Place the thermometer under your tongue as far back as you can comfortably put it. Keep your mouth closed and hold the thermometer in the same spot until the thermometer beeps.
5. Record the date, time (using a 12-hour clock with AM or PM), and temperature reading in the table below.
6. If you take your temperature more than once in a day, record the highest temperature.

	Day 1 (Vaccination)	Day 2	Day 3	Day 4	Day 5	Day 6	Day 7
Date (DD/MMM/YYYY)	____ / ____ / 202____	____ / ____ / 202____	____ / ____ / 202____	____ / ____ / 202____	____ / ____ / 202____	____ / ____ / 202____	____ / ____ / 202____
Time (HH:MM)	____ : ____  AM  PM	____ : ____  AM  PM	____ : ____  AM  PM	____ : ____  AM  PM	____ : ____  AM  PM	____ : ____  AM  PM	____ : ____  AM  PM
Temperature (°F)	_____. ____ °F						

ACV01 Vaccine Reaction Diary Card

Participant ID: _____

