INJECTION SITE SYMPTOM RECORD: Using the measuring tool provided at the time of your injection, rate the symptoms you experience in the table below. For each injection site symptom listed, mark either *Not Present* or circle the appropriate letter. Every day you must select either *Not Present* or record a rating for each symptom listed.

Directions:

1. Center the measuring tool over the injection site.
2. Note the letter (A, B, C or D) of the ring that holds the widest point of redness and/or swelling / hardness.
3. Circle the letter corresponding to each symptom in the table below. **Please select only one answer per box.**

Days After Vaccination	Day 1 (Vaccination)		Day 2		Day 3		Day 4		Day 5		Day 6		Day 7	
Date (DD/MMM/YYYY)	____/____/202____		____/____/202____		____/____/202____		____/____/202____		____/____/202____		____/____/202____		____/____/202____	
Injection Site Redness	 Not Present													
Injection Site Swelling / Hardness	 Not Present													

MEDICATION CHANGES: Have you changed or added any new medications this week (prescription and/or over-the-counter)?

Yes

No

If yes, record each new or updated medication below. If you need more space, record medications on a separate piece of paper and keep it with your diary.

Medication Name	Dose	Frequency	Start Date (DD/MMM/YYYY)	Stop Date (DD/MMM/YYYY)	Reason

ACV01 Vaccine Reaction Diary Card

Participant ID: _____

SYMPTOMS EXPERIENCED: Using the participant symptom rating scale provided, rate the symptoms you experience in the table below. If you have no symptoms, place an "X" in the *No Symptoms* box and leave all other boxes for that day blank. If you have one or more of the listed symptoms, use the rating scale to rate each symptom. Every day you must check either *No Symptoms* or record a rating (at minimum the applicable number: 0, 1, 2, 3; you may also write none, mild, moderate, or severe) for all of the symptoms listed. **CALL THE STUDY DOCTOR IF YOU EXPERIENCE ANY SEVERE (RATING #3) SYMPTOMS.**

SYMPTOM RATING SCALE:

- 0 No symptoms
- 1 Mild (present, but did not require over-the-counter or prescription medications; did not interfere with daily activities)
- 2 Moderate (required over-the-counter or prescription medications; caused some interference with daily activities)
- 3 Severe (required over-the-counter or prescription medications; significant, incapacitating discomfort preventing daily activities)

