9.2.1. Solicited Adverse Events

Participants are provided access to an electronic 7-day diary to aid in recording solicited local and systemic reactions to the vaccine, as well as symptoms of a potential allergic reaction, unsolicited AEs, and concomitant medications, including start and stop dates. The diary includes instructions for participants on how to take an oral temperature and how to measure injection site reactions. A paper copy of the diary may be provided for participants who do not have a device to access the electronic diary or as a backup collection tool. A member of the study team will review the information in the diary with the participant, including how to use and access the electronic diary, and will record adverse events on the CRF page as appropriate based on review of the diary.

Summary displays based on the maximum severity of solicited symptoms reported over the 7-day period will be presented in tables and graphically by study arm. Summaries of the diary entries over the 7-day period will also be presented by study arm.

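### The general 0–3 diary scale combines medicine need and interference in every grade with no tie-break, so solicited-symptom severity can be misclassified by an unknown amount

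*Protocol*

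**What the plan says.** Protocol 12.3.1.1 defines three grades for a symptom that is present. The lowest grade asks for neither treatment need nor limitation: "1 = Mild: Present, but did not require over-the-counter or prescription medications; did not interfere with daily activities". The middle grade, by contrast, asks for both together. The highest grade keeps the treatment condition and raises the limitation to incapacity: "3 = Severe: Required over-the-counter or prescription medications; significant, incapacitating discomfort preventing daily activities".

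The adult card (Protocol 20.3) repeats the scale, with the top grade given as "Severe (required over-the-counter or prescription medications; significant, incapacitating discomfort preventing daily activities". The same general scale stands on the three pediatric cards (20.4 to 20.6). On any day with symptoms the participant must "record a rating (at minimum the applicable number: 0, 1, 2, 3; you may also write none, mild, moderate, or severe" for every listed item.

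Two other places describe severity without a medicine clause. The first page of the adult card says to call the study doctor "If you have any severe symptom that prevents daily activity or requires medical care". Protocol 12.3.1.1.1 gives pediatric nausea and vomiting their own scale, with the top grade "3 = Severe: Prevents daily activity"; pediatric diarrhea is graded by stool count.

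On analysis, SAP 9.2 accepts the participant's 0–3 grade, and SAP 9.2.1 plans "Summary displays based on the maximum severity of solicited symptoms reported over the 7-day period", in tables and graphs by study arm. Neither contains a rule for re-grading or for discordant entries.

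**The concern.** A severity grade should give every reaction exactly one place. Here each grade sets two conditions that need not move together. Several listed items, such as fatigue, armpit lymph nodes, shortness of breath and limb swelling, may not call for medicine even when they stop a person's normal day. A participant in that position has to decide privately which half of the definition counts, and different participants may decide differently.

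At stake is the meaning of the planned reactogenicity display. If the entered grade reflects interference for some participants and need for medicine for others, the by-arm distribution of maximum severity mixes the two in proportions nobody can recover. The card is also inconsistent with itself: its first page describes a severe symptom worth a call without reference to medicine, while a later instruction to call for any rating of 3 depends on a scale that includes a medicine condition.

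**Working it through.** The plan states no figure on this point, so there is nothing to reproduce first. The check is an enumeration.

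**Inputs** (Protocol 12.3.1.1): medicine is required or not (2 levels); interference is none, some, or prevents activities (3 levels). This gives 2 × 3 = 6 combinations for a symptom that is present. Grade 1 is (not required, none), Grade 2 is (required, some), Grade 3 is (required, prevents). Each combination is matched to the grades with the two conditions joined by AND, then by OR, then on interference alone.

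| Medicine required | Interference | AND | OR | Interference alone |
|---|---|---|---|---|
| No | None | 1 | 1 | 1 |
| No | Some | no grade | 1 or 2 | 2 |
| No | Prevents | no grade | 1 or 3 | 3 |
| Yes | None | no grade | 1, 2 or 3 | 1 |
| Yes | Some | 2 | 2 or 3 | 2 |
| Yes | Prevents | 3 | 2 or 3 | 3 |

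Under AND, 3 of 6 combinations fit a grade and 3 fit none. Under OR, every combination fits, but 5 of 6 fit more than one grade, and an incapacitating symptom that required no medicine is both mild and severe. On interference alone, all 6 map to exactly one grade.

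**Illustration of size.** The documents give neither a severe-reaction rate nor the share of such reactions that require no medicine, so both are assumptions. Let *n* be participants in an arm, *p* the proportion whose symptom truly prevents activity, and *f* the share of these that required no medicine and were entered below 3. Then

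expected participants at Grade 3 = *n* × *p* × (1 − *f*).

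With *n* = 80 (the per-arm maximum in Adult Stage 2 and both pediatric stages):

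| *p* | *f* = 0 | *f* = 0.10 | *f* = 0.25 | *f* = 0.50 |
|---|---|---|---|---|
| 5% | 4.0 | 3.6 | 3.0 | 2.0 |
| 10% | 8.0 | 7.2 | 6.0 | 4.0 |
| 20% | 16.0 | 14.4 | 12.0 | 8.0 |

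For *p* = 10% the displayed rate runs from 10% down to 5%. The *f* = 0 column is a real possibility: it is what happens if everyone in this position rates by interference and enters 3.

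**The case against.** The strongest case against has four parts.

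First, a reader might infer that the results are miscounted, or that Grade 3 is too low by some fixed share such as 30 to 50%. The documents do not support that. The card forces a rating and also allows the word severe to be written, so a bedridden participant can enter 3. No rate is given from which a share could be derived, and any range must start at zero. This part stands in full.

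Second, the text speaks of medicine that was required, not medicine that was taken. Someone who needed medicine and took none can still be Grade 3. This narrows the gap to symptoms that needed no medicine; it does not close it.

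Third, a reader might infer that the authors clearly meant severity to follow function alone. The evidence is mixed: pediatric diarrhea and the lower nausea and vomiting grades are counts, and the first-page call prompt also mentions medical care. The point does not need that inference. It needs only the absence of a tie-break, and none is given.

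Fourth, there are safeguards and the consequences are limited. Staff go through the diary with the participant, a Week 1 review is scheduled, redness and swelling are also measured with a ring tool, and fever is recorded as a temperature. The first page of the card gives a separate prompt to call, including for any concern or question, so a reader who infers that severe symptoms would go unreported goes beyond the text. The Grade 3 trigger for ad hoc DSMB review concerns vaccine-related SAEs, not diary scores. All of this limits the effect. But staff who review the diary have no rule to apply either, so review does not make the grade consistent.

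**Conclusion.** The point holds as a defect in the stated grading rule. Neither natural reading of the semicolon gives every symptom one grade, and neither protocol, cards nor SAP resolves it. Because a rating is mandatory and is displayed as entered, solicited-symptom severity can be misclassified by an unknown amount, from zero upward.

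The direction is clear only for an incapacitating symptom that required no medicine: any error understates Grade 3. The other two unmatched combinations can be entered at different grades by different people. The counts above rest on assumed values of *p* and *f*.

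The reach is the descriptive maximum-severity displays, for adults and for pediatric items on the general scale. The primary endpoint and the separate pediatric nausea, vomiting and diarrhea scales are untouched. The safety endpoint for related events of Grade 1 or higher does not change so long as some rating of 1 or more is entered. This should be corrected, but it does not threaten the trial's main conclusions.

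**What to change.** - In Protocol 12.3.1.1 and on the general scale of all four cards, state that the level of interference with daily activities sets the grade, whether or not medicine was required. Keep medicine use as a separate record. Leave the pediatric nausea, vomiting and diarrhea scales as they are.
- Reconcile the description of a severe symptom in the first-page call prompt and in the rating-3 call instruction with the scale.
- In SAP 9.2.1, report severity by card version. For diaries already completed, state the ambiguity next to the display and cross-tabulate entered severity against recorded medicine use. Note that the diary's medication table asks only about changed or added medicines, so it can miss an existing as-needed drug and does not link use to a symptom and day.

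The cost is a wording change to the protocol, cards and electronic diary, plus a short SAP addition. The downside is that ratings before and after the change are not strictly comparable. Adult Stage 1 closed to enrollment on 15 August 2022, so its completed diaries can only carry the caveat and the cross-tabulation.

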12.3.1.1.1 Grading of Pediatric Gastrointestinal Solicited Adverse Events

Pediatric participants will grade nausea, vomiting, and diarrhea solicited adverse events using a 0-3 symptom-specific rating scale as noted below and in the Vaccine Reaction Diary for Pediatric Participants (Appendices 20.4, 20.5, 20.6):

Nausea/Vomiting

- 0 = No symptoms
- 1 = Mild: 1 to 2 times in 24 hours
- 2 = Moderate: > 2 times in 24 hours
- 3 = Severe: Prevents daily activity

Diarrhea

- 0 = No symptoms
- 1 = Mild: 2 to 3 loose stools in 24 hours
- 2 = Moderate: 4 to 5 loose stools in 24 hours
- 3 = Severe: 6 or more loose stools in 24 hours

12.3.1.2 Grading of Allergic Reactions

The investigator will grade severity of systemic allergic reactions on a scale of 1 to 5 according to criteria set forth in the Consortium of Food Allergy Research (CoFAR) Grading Scale modified for use in adults only (See Appendix 20.2 CoFAR Grading Scale for Systemic Allergic Reactions Version 3.0).

12.3.1.3 Grading of Liver Function Abnormalities

Liver function abnormalities will be graded using alternative criteria, which are based on the NCI-CTCAE version 4.0, and are defined relative to the upper limit of normal (ULN) as follows:

- Aspartate aminotransferase [AST] increased
 - Grade 1: >ULN – 3.0x ULN
 - Grade 2: >3.0x ULN - 5.0x ULN
 - Grade 3: >5.0x ULN - 20.0x ULN
 - Grade 4: >20.0x ULN
- Alanine aminotransferase [ALT] increased
 - Grade 1: >ULN – 3.0x ULN
 - Grade 2: >3.0x ULN - 5.0x ULN
 - Grade 3: >5.0x ULN - 20.0x ULN
 - Grade 4: >20.0x ULN
- Alkaline phosphatase [ALP] increased
 - Grade 1: >ULN – 2.5x ULN
 - Grade 2: >2.5x ULN - 5.0x ULN
 - Grade 3: >5.0x ULN - 20.0x ULN
 - Grade 4: >20.0x ULN
- Blood bilirubin increased
 - Grade 1: >ULN – 1.5x ULN
 - Grade 2: >1.5x ULN - 3.0x ULN
 - Grade 3: >3.0x ULN - 10.0x ULN
 - Grade 4: >10.0x ULN

12.3.1.4 Grading of All Other Events

The study site will grade the severity of all other AEs experienced by the study participants according to the criteria set forth in the NCI-CTCAE version 5.0 as deemed appropriate for the 5 adult autoimmune diseases and 4 pediatric autoimmune diseases, and use of background IS medications of interest in this trial. This document (referred to herein as the NCI-CTCAE manual) provides a common language to describe levels of severity, to analyze and interpret data, and to articulate the clinical significance of all AEs.

Adverse events will be graded on a scale from 1 to 5 according to the following standards in the NCI-CTCAE manual:

Grade 1 = mild adverse event

Grade 2 = moderate adverse event

Grade 3 = severe or disabling adverse event

Grade 4 = life-threatening or urgent intervention

Grade 5 = death

For grading an abnormal value or result of a clinical or laboratory evaluation (including, but not limited to, a radiograph, an ultrasound, an electrocardiogram, etc.), a treatment-emergent AE is defined as an increase in grade from Baseline or from the last post-Baseline value, that does not meet grading criteria. Changes in grade from Screening to Baseline will also be recorded as AEs if related to a study-mandated procedure, treatment, or change in treatment (but are not treatment-emergent). If a specific event or result from a given clinical or laboratory evaluation is not included in the NCI-CTCAE manual, then an abnormal result would be considered an AE if changes in therapy or monitoring are implemented as a result of the event/result.

For additional information and a printable version of the NCI-CTCAE manual, consult the NCI-CTCAE web site: https://ctep.cancer.gov/protocolDevelopment/electronic_applications/ctc.htm.

12.3.2 Attribution Definitions

Solicited AEs will be attributed as being related to the study-provided vaccine. The relationship, or attribution, of all other AEs to the study-provided vaccine or study procedure(s) will initially be determined by the site investigator and recorded on the appropriate AE eCRF. Final determination of attribution for safety reporting will be determined by the DAIT/NIAID Medical Monitor. The relationship of an AE to vaccine, study therapy regimen, or study procedures will be determined using the descriptors and definitions provided in [Table 16](#), Attribution of Adverse Events.

Table 16. Attribution of Adverse Events

Code	Descriptor	Relationship (to primary investigational product and/or other concurrent mandated study therapy or study procedure)
UNRELATED CATEGORY		
1	Not Related	The adverse event is clearly not related: there is insufficient evidence to suggest a causal relationship.
RELATED CATEGORIES		
2	Possibly Related	The adverse event has a reasonable possibility to be related; there is evidence to suggest a causal relationship.
3	Related	The adverse event is clearly related.

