 - Participant-Reported Outcomes Measurement Information System (PROMIS) 29 (adults only)
 - Pediatric Quality of Life Inventory™ (PedsQL) (pediatrics only)
 - Patient Global Assessment (PtGA)
 - Patient Global Impression of Change (PGI-C)
- The proportion of participants who experience the following safety events:
 - Any Grade 1 or higher AEs related to the additional doses of COVID-19 vaccine
 - Any SAEs, MAAEs, NOCMCs
 - Any SARS-CoV-2 infection

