7.1 Concomitant Medications

7.1.1 Protocol-mandated Medications

There are no protocol-mandated medications in this clinical trial. However, there is protocol-mandated temporary cessation as follows:

- Adult and Pediatric Stage 1 participants:
 - There will be a protocol-mandated temporary cessation of cohort-defining IS in **some** participants in Cohort A (MMF/MPA) and Cohort B (MTX).
- Adult and Pediatric Stage 2 participants:
 - There is a protocol-mandated temporary cessation of cohort-defining IS in **all** Cohort D (MMF/MPA) and Cohort E (MTX) participants.
 - Any participants in Cohort F (BCDT) who are also taking MMF/MPA or MTX will have a protocol-mandated temporary cessation of their MMF/MPA or MTX dose.

Adult and Pediatric Stage 1 in Cohort A: MMF/MPA and Cohort B: MTX that are randomized to hold these medications at the time of the additional homologous vaccine dose (per Section 3.1 Description of Study Design) and all Adult and Pediatric Stage 2 participants will be required to hold these medications as follows:

- Participants taking MMF/MPA (any dose) will hold the doses for 3 days before and 10 days after their vaccine dose.
 - Participants taking additional IS medications (such as tumor necrosis factor [TNF] inhibitors, JAK inhibitors, abatacept, belimumab, etc.) will be required to continue them during the time of the additional vaccine dose.
- Participants taking MTX (at any dose) will be required to hold their weekly dose for **at least 7 days before** their vaccine dose and for **at least 7 days after** administration of the vaccine. In total, the participant should not hold their MTX for more than 21 days.

- Participants taking additional IS medications (such as TNF inhibitors, JAK inhibitors, abatacept, belimumab, etc.) will be required to continue them during the time of their vaccine dose.

Participants that are randomized to continue medications (per Section 3.1 Description of Study Design) are required to maintain a stable dose of medication during the same period (Cohort A: MMF/MPA from 3 days before to 10 days after the additional homologous vaccine dose; Cohort B: MTX from 7 days before to 7 days after the additional homologous vaccine dose) unless they experience a change in disease activity requiring medication changes.

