12.2.1.3 Solicited Adverse Events (Reactogenicity)

Solicited AEs are predefined local and systemic events for which the participants will be specifically questioned, and which will be noted by these participants. In this study, queried symptoms will include:

- Injection site reaction such as pain, erythema, induration/edema as well as development of papules, and ulceration.
- Axillary lymphadenopathy.
- Solicited systemic reactions including fever (assessed as daily oral temperature), chills, myalgia, arthralgia, fatigue*, headache*, nausea*, vomiting, hives, and diarrhea.

*Participants that are 2-3 years old will have sleepiness, irritability/crying, and loss of appetite assessed rather than fatigue, headache, and nausea.

- Increased shortness of breath, chest pain**, swelling/pain in arm or leg**.

**These symptoms will be assessed in participants age 5 years and above.

- Increase in symptoms of the participant's underlying autoimmune disease.

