12.4.2 Increase in Autoimmune Disease Activity

Any increase in autoimmune disease activity (flare/relapse) for the participant's qualifying autoimmune disease will not be reported as an AE. These events will be collected and reported on the disease-specific assessment eCRFs. (Section 8.1.4.2 Disease-Specific Assessments).

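### Attributing every solicited symptom to the vaccine, with no pre-dose rating, labels unchanged chronic symptoms and symptoms of the medication hold as vaccine-related adverse events

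*Protocol*

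**What the plan says.** **Attribution.** Protocol 12.3.2: "Solicited AEs will be attributed as being related to the study-provided vaccine". The site investigator attributes only the remaining AEs, using Table 16.

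**What is solicited.** Protocol 12.2.1.3 lists "Solicited systemic reactions including fever (assessed as daily oral temperature), chills, myalgia, arthralgia, fatigue*, headache" and others, then increased shortness of breath, and then "Increase in symptoms of the participant's underlying autoimmune disease".

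**How it is graded.** Under Protocol 12.3.1.1, Grade 1 requires only that the symptom is present, needs no medication and does not interfere with daily activities. Nothing requires it to be new or worse.

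**When it is collected.** Protocol 12.4.1 starts collection at vaccination. The diaries (20.3 to 20.6) have columns for Days 1 to 7 only. The adult diary tells participants to "rate the symptoms you experience in the table below". Its shortness-of-breath line drops the qualifier that 12.2.1.3 carries.

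**Where it is used.** Protocol 3.3 has as a secondary safety endpoint the proportion with "Any Grade 1 or higher AEs related to the additional doses of COVID-19 vaccine". SAP 9.2.1 plans "Summary displays based on the maximum severity of solicited symptoms reported over the 7-day period" by study arm, with no baseline comparison.

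**The hold.** Protocol 7.1.1: "Participants taking MMF/MPA (any dose) will hold the doses for 3 days before and 10 days after their vaccine dose". MTX is held for at least 7 days on each side of the dose.

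**The other rule on worsening.** Protocol 12.4.2 says that an increase in activity (flare or relapse) of the participant's "qualifying autoimmune disease will not be reported as an AE"; it goes on disease-specific forms instead.

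**The concern.** The participants have RA, SLE, SSc, MS, pemphigus, JIA, JDM or POMS. Joint pain, muscle pain, fatigue and dyspnea can be part of daily life in several of these. The eligibility check on the day of vaccination (Protocol 8.1.3 and 8.2.4) turns away clinically active disease only if it leads to more immunosuppression (or suggests an MS relapse), so stable chronic symptoms are admitted. A participant whose usual joint pain continues unchanged through the diary week then has, by rule, a Grade 1 vaccine-related AE.

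The same rule applies to symptoms that appear because MMF/MPA or MTX was stopped, although Protocol 5.3.1 itself names exacerbation and flare as risks of stopping.

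At stake is the meaning of the related-AE rate and of the symptom-specific reactogenicity tables. There are two further effects. Protocol 12.5.1 requires a solicited AE still ongoing at Day 7 to be entered in EDC, and persistent symptoms are the ones most likely to be chronic. The MAAE definition (12.2.4) requires possible relatedness, which a diary symptom satisfies automatically.

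**Working it through.** The plan states no figure to reproduce. The check is a chain of rules, a day count, and an illustration with assumed inputs.

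**1. Rule chain.** Shared symptom on the solicited list (12.2.1.3) → rated from Day 1 with no earlier rating (12.4.1, diaries) → presence alone is Grade 1 (12.3.1.1) → related by rule (12.3.2) → counted in the endpoint (3.3). I looked for a step that removes pre-existing symptoms and found none:
- SAP 9.2 reports treatment-emergent AEs, but Protocol 12.3.1.4 defines that term only for abnormal clinical or laboratory results.
- The Medical Monitor makes the final attribution for safety reporting (12.3.2), but no rule tells the monitor to set aside pre-existing diary symptoms.
- SAP 9.2 lists vaccine-related AEs and solicited AEs as separate rows of the overall table. It does not say whether diary-only events enter the first row.

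**2. Overlap of hold and diary.** Day 1 is vaccination, so diary Day 7 is six days after it. The MMF/MPA hold runs to 10 days after and the MTX hold to at least 7 days after. Each covers 7 of 7 diary days.

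**3. Illustrative size.** Let v be the share with a true vaccine reaction, b the share with a pre-existing symptom on the list, and h the share with a hold-induced symptom, assumed independent.
- Continue arm: recorded share = 1 − (1−v)(1−b); inflation over v = b(1−v).
- Withhold arm: recorded share = 1 − (1−v)(1−b)(1−h); excess over continue = (1−v)(1−b)h.

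The values of b and h, and v = 20% and 40%, are assumptions. The value v = 74% is the share with local reactions in the 21-patient JIA vaccination study described in Protocol 1.2.3. It matters because the endpoint counts any related AE, including injection-site pain.

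| v | b = 10% | b = 30% | b = 70% |
|---|---|---|---|
| 20% | 28% | 44% | 76% |
| 40% | 46% | 58% | 82% |
| 74% | 77% | 82% | 92% |

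Inflation runs from 0.10 × 0.26 = 2.6 points to 0.70 × 0.80 = 56 points.

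With b = 30% and h = 10% to 20%:
- v = 40%: withhold 62.2% to 66.4% against 58% in the continue arm, an excess of 4.2 to 8.4 points.
- v = 74%: excess 0.26 × 0.70 × h = 1.8 to 3.6 points.

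**4. What can be separated.**
- Stage 1 Cohorts A and B are randomised 1:1 within the same vaccine, stratified by disease (3.5.1.1, 3.5.2.1). Terms v and b are common to both arms in expectation, so the withhold-minus-continue difference estimates the effect of the hold, including any effect on the vaccine reaction itself.
- Stage 2 Cohorts D and E are not randomised and everyone holds (3.5.1.2 and the Pediatric Stage 2 part of 3.5.2). There is one recorded proportion per arm and three unknowns.

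**5. The two rules on worsening.** Section 12.2.1.3 with 12.3.2 makes increased autoimmune symptoms a solicited and automatically related AE. Section 12.4.2 says a flare or relapse of the qualifying disease is not an AE. Neither says where a symptom increase becomes a flare, or which rule governs.

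**The case against.** **Automatic attribution is ordinary in reactogenicity work.** It is reasonable for injection-site reactions. The objection here is confined to symptoms shared with the underlying disease.

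**Baseline information exists.** PtGA, PROMIS-29 or PedsQL, joint counts and disease indices are scheduled at Baseline (20.1). They can give context, but they are not on the diary scale and no rule links them to solicited AEs.

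**Local reactions may dominate the endpoint.** This stands. At v = 74%, inflation of the any-AE rate is 0.26b, or about 3 to 18 points for b of 10% to 70%. A reader might infer that the endpoint mostly measures background disease. The documents do not support that: they give no background rate, and at b = 30%, v = 40%, 40 of the 58 recorded points are people with a true reaction.

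**Randomisation protects the hold comparison.** This also stands. A reader might infer that the trial cannot separate hold from vaccine effects anywhere. That is true of Stage 2 Cohorts D and E, but not of Stage 1 Cohorts A and B.

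**The open-ended diary question.** A reader might see a third conflicting rule, because the diary collects autoimmune worsening under additional symptoms. Section 12.2.2 makes an AE unsolicited only if it is not specified as solicited, and this item is specified. Its wording also already asks for an increase. The conflict is between two rules.

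**A single Day 1 pre-dose rating is not a sufficient correction.** It falls inside the hold, so it would remove early hold symptoms in withhold arms only and treat the arms unequally.

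**Conclusion.** The point holds as a labelling and interpretation problem in a descriptive secondary safety endpoint. Followed as written, the plan counts unchanged chronic symptoms and hold-related symptoms as vaccine-related. The amount cannot be calculated from the documents. The range of about 3 to 56 points rests on assumed symptom rates, independence, and diary events entering the related-AE count, which the SAP leaves open.

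In Stage 1 Cohorts A and B the hold's effect remains estimable and the error is the label. In Stage 2 Cohorts D and E, and for Cohort F members who also hold MMF/MPA or MTX, hold and vaccine symptoms cannot be told apart. The conflict between 12.2.1.3 with 12.3.2 and 12.4.2 needs no assumption and must be resolved. The primary endpoint and sample size are unaffected.

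**What to change.** 1. **Attribution text.** In 12.3.2, take the autoimmune-symptom item out of automatic attribution and have the investigator attribute it under Table 16. Reconcile 12.2.1.3 with 12.4.2 so that one rule says how increased symptoms and flares of the qualifying disease are recorded. State in the SAP whether diary-only events enter the related-AE count.

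2. **Future participants.** Rate the shared systemic symptoms on the diary scale at Screening, before any hold, and again on Day 1 before the dose. Report symptoms that are new or worse than the pre-hold rating in a table beside the any-grade table, not in place of it. The Day 1 rating shows what changed during the pre-dose part of the hold. A seven-day maximum will tend to exceed a single earlier rating even without real change, which is another reason to keep both tables.

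3. **Participants already enrolled.** Show joint pain, muscle pain and fatigue by disease and by IS plan, labelled as not baseline-corrected, with PtGA, PROMIS-29 or PedsQL and joint counts for context.

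**Cost.** A few minutes of extra rating per participant, one more table, and changes to protocol and SAP wording. It does not correct data already collected, including the Adult Stage 1 arms closed on 15 August 2022. Nothing in the dosing or hold rules changes.
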